## **7. Data and Specimen Banking**

De-identified interview-gathered questionnaire data regarding caregivers' psychological well-being and self-assessment of competency will be stored in REDCap for analysis. De-identified transcriptions of audio-recorded Aim 2 open-ended qualitative interviews will be stored on Emory's instance of Box, accessible only to the study investigators. All study participants will be assigned ID numbers. The file linking identities to IDs will be stored separately on the PI's encrypted work computer. De-identified transcriptions of audio-recorded Aim 1 design sessions will also be stored on Emory's instance of Box, accessible only to the study investigators.

The final dataset will include standardized measures of caregiver well-being and competence and will be stored in PI [name]'s office in the Emory University Nell Hodgson Woodruff School of Nursing in Atlanta, Georgia. Data from this study will be available to qualified researchers through a data sharing agreement that is fully consistent with NIH data sharing policies and applicable laws and regulations as well as official policies and practices established by the Roybal Center at Emory. Although these data will be de-identified prior to release for sharing, there remains a possibility of deductive disclosure of participants with unusual characteristics. Therefore, this data sharing agreement will require: 1) a commitment only to use the data for research purposes and not to identify any individual participant; 2) a commitment to securing the data using appropriate computer technology; and 3) a commitment to destroy or return the data after analyses are completed.

## **8. Sharing of Results with Participants**

Results of each Design Studio will be shared with participants as each iteration of the course is developed. At study's end, we will prepare a lay report detailing the results of the study and distribute this report to study participants.

## **9. Study Timelines**

For those caregivers engaged in the Aim 1 portion of the study, this will be a one-time involvement, lasting only during their participation in one of the Design Studio exercises. This will take approximately 1-2 hours

For any caregiver engaged in the Aim 2 wait-list control trial of the prototype developed in Aim 1, participation will last approximately 5 months.

We expect Aim 1 recruitment and enrollment to occupy a span of approximately 5 months, and Aim 2 recruitment and enrollment – which will begin while we are still engaged in Aim 1 activities – is expected to span about 5 months, from project month 4-9.

The study as a whole will take one year. Aim 1 activities will be complete by the end of the fifth month; Aim 2 activities will be completed by project's end.

## **10. Subject Population**

We will seek to enroll family members (or friends) who self-identify as a principal caregiver and the principal companion of a community-dwelling PLWD during healthcare encounters. We will provide verbal and written instructions in how to access and use the course, provide a schedule for their completion of the course over the next 6-8 weeks, and mail out course materials. At the end point of each wave, we will purposively select 10 caregivers to participate in semi-structured interviews (total n=20) based on varying caregiver characteristics and findings from baseline quantitative data (e.g., stress levels, gender, race/ethnicity). Interviews will last approximately 45 minutes and will ask questions about the overall contribution of the course to their own perceived sense of competence as caregivers and healthcare navigators during the pandemic. We will also seek their responses to the course (Acceptable? Usable? Relevant? Enough? Too much? What's missing? How to improve?). We will provide \$25 gift cards for participation in each baseline focus group and post-intervention semi-structured interview.

Caregivers would be excluded if their loved one is institutionalized or receiving hospice services or there are plans to do so within the next three months. Participants must also be able to read and speak English and be able to access the online course materials.

## **11. Vulnerable Populations**

---

The study does not include individuals who lack decision-making capacity or may be susceptible to undue influence or coercion.

## **12. Local Number of Participants**

We plan to recruit 30 participants in phase 1 of the study, designing the course, and 100 participants in phase 2, testing the course. All participants will be recruited from networks in Georgia.

## **13. Recruitment Methods**

Core pilot team members can draw on their multiple involvements as recruitment sources for a diverse group of caregiver to address Aims 1 and 2. MPI [name]'s IMCC has patient panel of >600 and a very active Family Advisory Board that has been integrally involved in the development and vetting of all aspects of the IMCC. The statewide Georgia Memory Net serves >300 dementia families, many in rural Georgia ([name]). Emory's NIA-supported Alzheimer's Disease Research Center ([name], Co-I) maintains a large registry of caregivers willing to be contacted. Core team members' ongoing work with African American church communities ([name]), MCI empowerment activities ([name]), and MPI [name]'s near-completed Tele-Savvy project can further ensure successful recruitment from program completers (25% African American).

Direct care providers (physicians, nurse practitioners) *will not* recruit participants.

### Recruitment and Recruitment Materials for Aim 1 Design Studio Activities.

Caregivers who engage in the Design Studio process of developing the Caregiving During Crisis are not taking part in the research study. We will use the personal and organizational contacts described in the paragraph above to identify participants. For example, we expect to draw on advisory board members from the IMCC and MCI empowerment center, as well as community advisors to the Emory Roybal Center to take part in these design activities. Invitations will be made through phone calls and emails directly to these individuals.

### Recruitment and Recruitment Materials for the Aim 2 Randomized Control Trial.

We plan to draw on the contacts available to each of the study investigators and to the broader networks with which they are affiliated (e.g., the national Alzheimer's Disease Centers and Roybal Centers) to provide information to potential participants. Potential subjects will be contacted by email if they have indicated their willingness to receive information about studies that might be of possible interest.

We will advertise online, through Social media, such as Twitter, Facebook and Instagram, and through Emory Healthcare on-hold message services. We will ask organizations in our network to use their normal methods of communication (e.g., their newsletters) provide a link to the study announcement which will be posted on our Roybal Center website (emorycaregiving.org). These announcements and scripts are attached to this application in the Recruitment Materials section.

### Eligibility Determination

Screening will be conducted by distance means (phone or videoconference) by investigators [name] or [name] or Roybal Program Manager [name].

- Is the potential subject providing care for a family member or friend? If so:
  - Does that person have a confirmed diagnosis of dementia?
  - Is the person living in the community?
  - Is the caregiver co-residing with the person?
  - Is the caregiver the main caregiver for the person?
- Does the caregiver have a computer with internet access?
- Can the person read and understand English?

The screening calls or videoconferences will not be recorded. No identifying information about the screening calls, including the person's IP address, will be recorded.

### Payments to Participants

We will provide \$25.00 gift cards (e.g., Visa cards) to participants for each interview in which they take part. All trial participants will be asked to take part in a baseline interview and then subsequent interviews 3 and 5 months later. About 20% will be asked to take part in focus groups prior to their enrollment in the course, and about 20% will be asked to take part in semi-structured interviews following course completion. Thus, the maximum payment for any participant would be \$100.00

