Early findings from the synchronous/asynchronous online three-arm randomized Tele-Savvy trial provide encouraging support for this project. The online Tele-Savvy psychoeducational caregiving course we propose appears to work and caregivers do fully participate in its asynchronous component. We used multilevel mixed models to test for group, time, and group-by-time effects for each of the outcomes. Results from the first 220 participants in the baseline to six-month segment of this three-arm trial indicate that Tele-Savvy participants had statistically significant group-by-time reductions in depression and strain and statistically significant group-by-time increases in caregiver mastery, compared to those in the other two study arms. We found a significant group-by-time effect on CES-D-assessed caregiver depression ( $p<.001$ ) with the active group showing significant decreases over time ( $p<.001$ ). We found a significant group-by-time effect on caregiver perceived strain ( $p<.001$ ) with the active group demonstrating significant reductions over time ( $p<.001$ ) and the waitlist control group demonstrating significant increases ( $p=.010$ ). Likewise, there was a significant group-by-time effect ( $p=.001$ ) on caregivers' reactions to care recipient behaviors (RMBPC) with significant reductions over time among the active caregivers ( $p=.001$ ). Caregiver competence likewise demonstrated a significant group-by-time effect ( $p=.009$ ), with the active group demonstrating significant increases over time ( $p<.001$ ). Findings regarding caregivers' mastery were comparable: a significant group-by-time effect ( $p=.003$ ) with the active group demonstrating significant increases over time

(p<.001). Canvas-based analytics indicate that participants were highly adherent in viewing the 36 asynchronous 8-15 minute daily video lessons, spending, on average, more than 8 hours watching the videos over the course of the 43-day program.

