## **17. Data Analysis, Management and Confidentiality**

Quantitative data will be entered at the time of each Aim 2 interview directly into the dedicated project tablet computer and saved on Emory's secure REDCap platform. All data entry screens are set up in REDCap and, where possible, include data delimiters (i.e., skip patterns, valid range limits) to ensure correctness and minimize missing data. Data will be exported weekly and analyzed for data cleaning and verification. Upon completion of each cohort data-gathering point, all data will be merged for scale computation, aggregation, and analysis. We will use NVIVO 12 software to store and manage all qualitative data and to facilitate data analysis.

For quantitative analysis, we will test for group, time, and group-by-time effects for each of the outcomes (caregiver anxiety, depression, burden, stress, and mastery). In preliminary analyses, descriptive statistics and frequency distributions will be examined to identify outliers and ensure integrity of all data. For all multi-item scales, internal consistency will be examined using Cronbach's alpha and associated statistics (e.g., item-total correlations, alpha if item deleted). Preliminary analyses will examine baseline differences among completers and non-completers and by study arm (immediate/delayed) as a randomization check using 2-group comparison tests (t-tests and non-parametric equivalent tests for continuous variables (normally or non-normally distributed) and Chi-Square tests for categorical variables). The association of predisposing factors (demographics, Caregiving history, relationship and care recipient status at baseline) with changes in outcomes over time will be examined to identify significant covariates. Where significant associations with baseline measures are detected, these potential confounders will be controlled for in subsequent analyses using covariate model adjustments.

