We will use repeated measures analysis to test 2 time by 2 group intervention (Immediate Participation in wave1 + immediate participation in wave 2) vs waitlist control (wave 1 + wave 2) change from baseline to post intervention at 8 weeks elapsed. Given final expected sample sizes of 45 subjects in each group (assuming 10% attrition), we will be powered at 80% with a 5% level of significance to detect moderate-to-large effect sizes for the group ( $f=0.297$ ), time ( $f=0.300$ ), and group-by-time ( $f=0.300$ ) effects. To examine intervention effects over time for the combined intervention groups (Immediate wave 1 (week 16-24) + Immediate wave 2 (week 24-32) + waitlist wave 1 participants after course participation (week 24-32)), we will use repeated measures mainly focused on pre-to-post intervention effects for the 3 groups combined, however a group effect will be tested to ensure that the WLC1 had no placebo carryover effect that altered their "baseline at 24 weeks" from the other 2 groups. Given the

sample sizes of 25 subjects in each of these 3 groups, we will be powered at 80% with a 5% level of significance to detect moderate-to-large effect sizes for the group ( $f=0.381$ ), time ( $f=0.381$ ), and group-by-time ( $f=0.381$ ) effects.

To address Aim 2 formative questions, Co-Investigator [name] will lead the team in a thematic analysis of the transcribed baseline focus group and post-intervention semi-structured interviews. We hope to pursue three lines of inquiry in this analysis that will be crucial for the next steps in our work: (1) In what ways might the overall concept of caregiver as healthcare navigator be sharpened? (2) In what ways might the delivery mechanism of the course be enhanced to improve caregiver learning (e.g., more interactivity)? (3) In what ways might individual components of the course be enhanced to improve caregiver learning (e.g., different formats; additional videos)? We expect that these analyses will provide compelling evidence for the feasibility, acceptability, and usability of the course.

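### The pooled three-group pre-to-post analysis counts untreated change as course effect, over intervals that are probably unequal, and its planned group terms cannot reveal this

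*Combined protocol and SAP*

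**What the plan says.** Section 17 plans two quantitative analyses. The first compares the randomised arms on "change from baseline to post intervention at 8 weeks elapsed". The second pools "Immediate wave 1 (week 16-24) + Immediate wave 2 (week 24-32) + waitlist wave 1 participants after course participation (week 24-32") and uses "repeated measures mainly focused on pre-to-post intervention effects for the 3 groups combined". For this pooled analysis it adds that "a group effect will be tested to ensure that the WLC1 had no placebo carryover effect that altered their" starting level at 24 weeks, and it quotes detectable effects for group, time and group-by-time with 25 participants in each of the three groups. No term for elapsed time is named. The covariate search concerns "The association of predisposing factors (demographics, Caregiving history, relationship and care recipient status at baseline) with changes in outcomes over time", which does not include interval length.

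The timing is described in several places:

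- **Section 6 (Aim 2):** random assignment takes place only after every participant in the wave has had a baseline interview. The second interview comes at the 8-week point, after the immediate group's course and before the waitlist group enrols. The third follows 8 weeks later.
- **Section 13 (Payments to Participants):** "All trial participants will be asked to take part in a baseline interview and then subsequent interviews 3 and 5 months later".
- **Section 9:** participation lasts about 5 months.
- **Section 1:** the individual duration is 24 weeks.

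**The concern.** In a pooled pre-to-post analysis the time effect is the course effect plus whatever would have happened anyway. The plan's own background indicates that the second part need not be zero. In the earlier Tele-Savvy trial, strain changed without the course, with "the waitlist control group demonstrating significant increases" (p=.010). If untreated caregivers worsen, the pooled estimate understates benefit. If an outcome improves unaided, the estimate overstates it.

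The pre measures also differ in kind. The immediate groups' only pre-course interview is baseline, taken before an unstated delay to course start. Waitlist wave 1's pre measure is the second interview, taken just before enrolment. The immediate groups' interval therefore contains untreated waiting time that waitlist wave 1's does not. A group test meant to detect carryover would respond to this timing difference as well.

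**Working it through.** **1. The plan's own figures.** Using a noncentral F with noncentrality f² × N, the randomised analysis (N=90, f=0.300) gives power 0.804, as stated. For the pooled analysis (N=75, f=0.381) the result is 0.833 with 2 numerator degrees of freedom and 0.902 with 1, not 0.80. The figure 0.381 fits about 23 per group (0.797). Nothing below depends on it.

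**2. Intervals.** One month = 365.25/12/7 = 4.348 weeks.

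| Source | Immediate groups (n=50) | Waitlist wave 1 (n=25) |
|---|---|---|
| Section 6 | 8 weeks + lag (length not given) | 8 weeks |
| Section 13 | 3 × 4.348 = 13.0 weeks | (5 − 3) × 4.348 = 8.7 weeks |
| Section 17 | 8 weeks | 8 weeks |

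A lag of 13.0 − 8 = 5 weeks reconciles Sections 6 and 13: interviews would fall at 13 and 21 weeks, against 13.0 and 21.7. Without a lag, two 8-week segments end at 16 weeks (3.7 months), short of Section 9's 5 months and Section 1's 24 weeks. Section 17's week labels do not settle the matter, because they start wave 1's course at week 16 while Section 6 places wave 1 baseline data at about week 22.

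On Section 13's figures the pooled mean interval is (50 × 13.04 + 25 × 8.70)/75 = 11.6 weeks.

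**3. Size of untreated change (assumed).** The only source is the waitlist strain result, p=.010, from "Results from the first 220 participants in the baseline to six-month segment of this three-arm trial". The arm size is not given, so I take 44 to 110, with 73 for equal arms. I treat the p-value as a paired t test and the change as linear over 26.1 weeks. SD per week = t/√n/26.1.

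| Assumed n | t | SD over 6 months | SD per week | Whole pooled interval (× 11.6) | Extra month only (× 4.348 × 50/75) | If all intervals are 8 weeks (× 8) |
|---|---|---|---|---|---|---|
| 44 | 2.695 | 0.406 | 0.0156 | 0.18 | 0.045 | 0.12 |
| 73 | 2.646 | 0.310 | 0.0119 | 0.14 | 0.034 | 0.09 |
| 110 | 2.622 | 0.250 | 0.0096 | 0.11 | 0.028 | 0.08 |

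For scale, 75 participants can detect a paired change of 0.328 SD (80% power, two-sided 5%). The whole drift is 0.11/0.328 = 34% to 0.18/0.328 = 55% of that. The extra month is 8.5 to 13.8%.

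**4. Can the planned terms show it?** The extra month makes change differ between groups by 4.348 × 0.0096 = 0.04 to 4.348 × 0.0156 = 0.07 SD. A 50 versus 25 contrast has power 5.3% at 0.04 SD and 6.2% at 0.08 SD, barely above the 5% error rate. Drift common to all three groups does not appear in any between-group term.

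**5. What a drift-adjusted analysis does.** With an assumed true effect of −0.33 SD, the planned estimate is centred at −0.33 + 0.11 = −0.22 to −0.33 + 0.18 = −0.15. In simulation, a model with actual elapsed time recovers −0.33. Its standard error can be checked roughly. The planned analysis has 1/√75 = 0.115. The drift from 50 waitlist participants has 1/(√50 × 13.04) = 0.0108 per week, or 0.126 over 11.6 weeks. Together √(0.115² + 0.126²) = 0.17, treating the two parts as independent. A simulation (drift 0.0116 SD per week, lag 0 to 10.1 weeks, no attrition) gave 0.169.

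**The case against.** The strongest reply is that unequal intervals are not established. Section 17 says 8 weeks, no passage links Section 13's 3 months to a lag, and Section 13 speaks in whole months. If 3 and 5 are each rounded to the nearest month, the first gap is 2.5 to 3.5 months and the second 1 to 3, so their ratio could be anywhere from 0.83 to 3.5. This stands. Unequal intervals are the likely reading, because Section 6 makes assignment wait for the whole wave's baselines, but they remain an inference.

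A reader might infer that the pooled model has no term in which a group difference in change could appear. It does: Section 17 tests group and cites group-by-time. What remains is that these terms cannot say why groups differ, and that they have almost no power for a difference this small.

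A reader might also infer that the bias flatters the course. The only untreated change reported is worsening strain, which would mask benefit. Applying that one outcome to the others is an assumption.

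Finally, the unequal month is the lesser part. Most of the drift comes from having no concurrent control and would remain with equal intervals. That is correct, and it is why the remedy addresses drift over the whole interval. This is also a secondary analysis in a pilot of preliminary efficacy, which limits the consequences.

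**Conclusion.** The point holds as a minor weakness of the pooled analysis. That analysis attributes untreated change to the course, over intervals that are probably about 3 months for 50 participants and 2 months for 25. If strain drifts upward linearly at the rate implied by the earlier trial, the estimate is biased toward no benefit by 0.11 to 0.18 SD of change, or 0.08 to 0.12 SD if every interval is 8 weeks. These sizes rest on an assumed arm size, linear change, a paired-t reading of a mixed-model p-value, and no attrition. The documents themselves give no size.

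A non-significant group test would not show that carryover is absent, and a significant one could reflect timing.

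A reader might extend this to the main comparison, but the documents do not support that. Both randomised arms share the lag, and Section 6 keeps the waitlist arm untreated until after the second interview.

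**What to change.** 1. Keep the planned pooled analysis. In Section 17, name the pre and post interview for each of the three groups.
2. Record each participant's interview and course-start dates, and report the pre-to-post interval by group.
3. Add a sensitivity analysis that models actual elapsed time and estimates untreated change from both waitlist groups' first interval (50 participants, already to be collected). State its assumption that untreated change continues at the same rate during the course.
4. State that a non-significant group test will not be read as evidence of no carryover.
5. Reconcile the interview timing in Sections 1, 6, 9, 13 and 17. Give the expected lag from baseline to course start and the origin of Section 17's 8 weeks.

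The cost is date recording and one additional model, with no added participants or interviews. The sensitivity estimate is less precise (standard error about 0.17 against 0.115 SD), so it should accompany the planned analysis and not replace it.

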## **14. Withdrawal of Participants**

Aim 2 study participants may request, verbally or via course message or email, to withdraw from the study at any time. Likewise, the study team may also withdraw a participant if their caregiving situation changes (e.g., if the person for whom they are providing care is institutionalized or dies).

## **15. Risks to Participants**

We believe that caregivers taking part in the trial of the Caregiving During Crisis program will be exposed to very low risks. The two main risks are of transient emotional distress and breach of confidentiality. These are described below.

Transient emotional distress. As persons providing care to a person living with dementia and doing so under the strains of the threat and restrictions of a pandemic, subjects in this study are already very likely to be experiencing a higher than normal level of stress and distress. The content of the course will draw their attention to their situation in ways that might make them more acutely aware of their distress or cause them to lower the defenses they might have

erected to fend off the distress. Likewise, the subject matter raised and the questions posed in the research interviews, the focus groups, and semi-structured interviews may also call attention to distressing matters and situations.

Based on our research experience with similar study subjects and the same questions and methods, we judge the occurrence of such distress to be relatively infrequent (perhaps in 25% of cases), of low magnitude (perhaps a 2 on a scale of 10, where 10 is the highest), of very brief duration, and fully reversible. The research interviewer will be trained to recognize such events and to provide ways to back away from and calm them. The participating investigators who would conduct the focus groups or semi-structured interviews are experienced in working with dementia caregivers and in managing such transient events in ways that permit the caregiver to work through them in a brief, respectful, and calming manner.

We can see no procedures in the study that might produce currently unforeseeable risks, and we can see no procedures that might put others at risk who are not in the study.

